2.1 Participants

This single center, prospective, open label study will enroll adults diagnosed with cerebral palsy aged 13 to 65 years, including a case-by-case basis of including those under the age of 13 years old, with a target sample size of 10 participants.

Most subjects will be recruited from [name] Medicine & Rehabilitation clinic. [name] will approach eligible patients in order to explain the study and to determine interest. Other physicians will also approach eligible patients and will explain the study. A brochure/flyer will be presented to each eligible and interested patient, with the study team's contact information on it for their reference. If they are interested and eligible right away, patients will be asked to fill out the consent form and provide us with their contact information so that we can contact them to schedule their initial assessment visit. Other recruitment methods include use of brochures/flyers in other departments in the hospital/CP Center. There will be no screening over the phone or via email.

2.2 Outcome Measures

Primary Question: Does Amantadine have an effect on cognitive function in 10 adolescents and adults diagnosed with cerebral palsy (CP)?

Hypothesis: If 10 adolescents and adults receive Amantadine, then cognitive function will increase/improve.

Secondary Question: Does Amantadine have an effect on fine and gross motor skills, and mood?

Hypothesis: If 10 adolescents and adults receive Amantadine, then there will be increased fine and gross motor skill function and improved rigidity, and mood scores will improve on the PHQ-9.

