1. INTRODUCTION

Cerebral palsy (CP) is a heterogeneous condition due to injury to the developing brain. It is a condition that is often marked by both cognitive and motor disorders as well as increased prevalence of depression and anxiety. While most studies have focused on improving motor dysfunction, fewer have investigated cognitive impairments associated with CP. Dedicating a study to research the pharmacotherapeutic effect of Amantadine on cognitive function in adolescents and adults with cerebral palsy fills an important gap in development of a potential innovative treatment for cognitive deficits.

This study's approach to treatment is aimed at improvement of cognitive function in primarily the adolescent and adult CP population, something that has not been wholly addressed by the research community to date. In the rehabilitation outpatient setting, we have used Amantadine in children and adults with CP for its dopaminergic properties. Amantadine, initially used as an anti-viral drug, is well supported in the literature for its efficacy in treating acute traumatic brain injury (TBI) to improve alertness, arousal, consciousness, mobility and improve rate of recovery. Based on the success of Amantadine in the TBI population, there are implications for its use in the cerebral palsy population because of the similar etiology of brain injury, but in the developing brain. The aim of this study is to determine the effects of Amantadine in primarily adolescents and adults with CP and to compare pre- and post-intervention outcomes related to the primary goal of improving cognitive function, focused on processing speed and attention span. We will also evaluate secondary goals of improving gross and fine motor skills as well as change in mood since Amantadine controls rigidity that could help functional mobility

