2. DESIGN

This single center, prospective, open label study will enroll adolescents and adults diagnosed with cerebral palsy, aged 13-65 years, and case-by-case assessment for children under the age of 13 years old, with a target sample size of 10 participants. A baseline assessment of the following domains will be conducted: cognitive function, gross motor & fine motor function, and mood/psycho-social function. Participants will start a daily regimen of Amantadine: dosing 2-5 mg/kg divided by two daily doses (max daily dose of 300 mg). Participants and caregivers will be given a diary to document their perceived effects of Amantadine.

At 3 and 6 weeks, we will repeat the assessments done in the pre-test to evaluate the efficacy of Amantadine. See below for assessment tools, performed as able according to participants' functional status:

1. Cognitive function: NIH Toolbox (Cognitive Battery)
2. Mood: Patient Health Questionnaire-9 (PHQ-9), BRIEF-A
3. Gross motor function: Berg Balance Test, Timed Up and Go, Modified Ashworth Scale, Modified Tradieu Scale, Passive Range of Motion
4. Fine motor function: Box and Blocks
5. Subjective self-assessment: Patient self-assessment of changes in attention, processing and motor skills

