2.3 Procedures

A baseline assessment of the following domains will be conducted: cognitive function, gross motor and fine motor function, and mood/psycho-social function. Because the PHQ9 assessment asks a question regarding suicide ideality, we will promptly review it each time it is completed, and if suicide ideality is reported, the subject will be provided with appropriate resources.

Participants will start a daily regimen of Amantadine: dosing of 2-5 mg/kg divided by two daily doses (max daily dose of 300 mg). Participants and caregivers will be given a diary to document their perceived effects of Amantadine. At 3 and 6 weeks, we will repeat the assessments done in the pre-test to evaluate efficacy of Amantadine.

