2.4 Statistical Analysis

No power calculations were made since there is no previous study that used the same population (adolescents and adults), with the same intervention (Amantadine), to find the same outcomes (cognitive and motor function).

The results will be statistically analyzed by using the paired samples t-test on SPSS.

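### The primary hypothesis names neither the cognitive score nor the visit that decides it, so both could be chosen after the data are seen

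*Combined protocol and SAP*

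**What the plan says.** Section 2.2 sets the primary question, "Does Amantadine have an effect on cognitive function in 10 adolescents and adults diagnosed with cerebral palsy (CP"), and a directional hypothesis: if participants receive amantadine, "then cognitive function will increase/improve". It names no score, time point or threshold.

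The other sections narrow this only in part:

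- **Instrument.** Section 2 lists "Cognitive function: NIH Toolbox (Cognitive Battery"). It chooses no subtest, composite or score type. The list is introduced with "See below for assessment tools, performed as able according to" each participant's functional status, so some scores may be missing.
- **Focus.** The Introduction gives the aim as "to compare pre- and post-intervention outcomes related to the primary goal of improving cognitive function, focused on processing speed and attention span". That is two constructs, neither ranked nor tied to a score.
- **Visits.** Section 2 says "At 3 and 6 weeks, we will repeat the assessments done in the pre-test to evaluate the efficacy of Amantadine", and section 2.3 repeats it: "At 3 and 6 weeks, we will repeat the assessments done in the pre-test to evaluate efficacy of Amantadine". Neither visit is called primary.
- **Analysis.** In section 2.4 the only statement of method is "The results will be statistically analyzed by using the paired samples t-test on SPSS". It gives no alpha, sidedness, order of testing or multiplicity rule.

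**The concern.** A paired t-test compares two time points, and this design has three (baseline, week 3, week 6). The stated method cannot be run on the primary hypothesis until someone picks the score and the pair of visits, and the plan leaves both open.

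If they are picked after the data are seen, a significant improvement on one focus score at one visit can be reported as supporting the primary hypothesis while the other results are passed over. The p-value attached to that result would then understate how often such a finding arises by chance. With a target of 10 participants, a single favourable score is easily over-read.

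**Working it through.** The plan states no alpha, power or error rate, so there is no figure of its own to reproduce. Section 2.4 says that no power calculation was made. The check asks how much freedom the text leaves and what that freedom could cost.

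**Inputs from the documents**

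- Target sample size 10, single arm (section 2).
- Two post-baseline efficacy visits (sections 2 and 2.3).
- Two focus constructs (Introduction).
- Paired t-test (section 2.4).
- Directional hypothesis (section 2.2).

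**Assumptions not in the documents**

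- Each test is two-sided at 0.05.
- Both visits are tested against baseline.
- Any significant improvement counts as support.
- True mean change is zero.
- All 10 participants are measured, and changes are normally distributed.
- Week-3 and week-6 changes correlate at 0.3 to 0.9, and the two scores at 0 to 0.8.

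**Number of tests.** Scores × visits: 1 × 2 = 2, or 2 × 2 = 4.

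**Single test.** Improvement is declared if t = mean change / (SD of change / √10) exceeds the critical value t(9) = 2.262. Under no change this happens with probability 0.05 / 2 = 0.025.

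**Independent tests, as a reference.** 1 − 0.975² = 0.049 for two tests, and 1 − 0.975⁴ = 0.096 for four.

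**Correlated tests.** Simulation with 400,000 runs per setting gives the chance of at least one false significant improvement:

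| Visit correlation | One score | Two scores, score corr. 0 | Two scores, corr. 0.5 | Two scores, corr. 0.8 |
|---|---|---|---|---|
| 0.3 | 4.8% | 9.4% | 8.8% | 7.6% |
| 0.5 | 4.6% | 9.0% | 8.4% | 7.3% |
| 0.8 | 4.0% | 7.9% | 7.3% | 6.4% |
| 0.9 | 3.6% | 7.1% | 6.6% | 5.8% |

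The ranges are 3.6-4.8% for one score and 5.8-9.4% for two, against 2.5% for one test.

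**Sidedness.** Because it is unstated, the baseline could differ. If each test were one-sided at 0.05, the ranges would be 6.9-9.4% and 10.6-17.8%, against 5%.

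**After the fix.** One named score at one named visit, or a fixed sequence that starts there, returns the rate to 2.5%. Two equally weighted tests at two-sided 0.025 each give at most 2 × 0.0125 = 2.5%. For one score at two visits the simulated range is 1.9-2.5%.

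**Detectable change.** The mean change detectable with 80% power (noncentral t, two-sided), in units of the SD of change:

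- 10 completers at 0.05: 1.00 (0.996).
- 10 completers at 0.025: 1.14 (1.139).
- 8 completers at 0.05: 1.16 (1.156). The figure of 8 is illustrative.

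**The case against.** The strongest reply is that the size rests wholly on assumptions. The plan gives no alpha, number of scores, correlations or rule that any significant result counts. This is right: the percentages are illustrations and contradict no figure in the plan. The omission itself needs none of them.

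A second reply is that a pre/post comparison by paired t-test suggests one comparison, most naturally with week 6. With one score fixed in advance, that reading gives no inflation. But the plan does not say which visit is the post-treatment one, and it uses both visits to evaluate efficacy.

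A third is that in a small, uncontrolled, open-label study this is not the main threat. If practice or expectation alone moved the mean by 0.3 or 0.5 SD of change (illustrative values), a single pre-specified test would show improvement in about 13% or 29% of such studies. Both exceed the 9.4% upper figure above. This stands, and it limits what the fix can deliver. It does not excuse the gap, because the plan labels a primary hypothesis and commits to a significance test.

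Two stronger readings should be resisted:

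- A reader might infer that any score in the whole battery could decide the hypothesis, and multiply the tests accordingly. The documents give no score count, and the Introduction narrows the focus to two constructs, so larger counts have no basis here.
- A reader might also quote the chance of a significant change in either direction (7.2-9.6% for one score, 11.5-18.2% for two, against 5%). Those figures include worsening, which could not support a hypothesis of improvement.

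**Conclusion.** The concern holds as an omission that should be fixed. None of the sections names the primary cognitive score or the primary visit, and no rule governs more than one test. Confidence in that is high, because it rests on the text alone.

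The size is moderate and conditional. Under the listed assumptions, a false significant improvement is roughly 1.4 to 1.9 times as likely as with a single test for one score (3.6 / 2.5 to 4.8 / 2.5), and 2.3 to 3.8 times for two scores (5.8 / 2.5 to 9.4 / 2.5). The one-score figure stays below 5% in absolute terms. The documents do not show that selective reporting is intended. They show only that nothing in the plan prevents it.

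**What to change.** Amend sections 2.2 and 2.4 before results are examined:

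1. Name one primary score, including its score type, that measures processing speed or attention, the focus given in the Introduction. Among scores that fit, prefer one that most participants can complete. The choice is the sponsor's.
2. Name one primary visit, for example change from baseline to week 6, tested by the two-sided paired t-test at 0.05.
3. If the other focus score or the other visit also matters, test it in fixed sequence, only after the first test is significant.
4. If two scores at one visit, or two visits for one score, must count equally, test each at 0.025.
5. Label all other battery scores and the motor and mood results secondary or exploratory, and report mean change with 95% confidence intervals. P-values for the stated secondary hypotheses may stay.

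The cost is wording only, with no added visits or participants. In return, no primary claim can rest on a score or visit outside the named plan. Participants who cannot complete the chosen score leave the primary test, which raises the detectable change as shown above (1.00 to 1.16 SD if 8 of 10 complete). The equal-weight option raises it from about 1.00 to 1.14 SD with 10 completers.

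The amendment does not by itself allow an improvement to be attributed to amantadine, because practice and expectation effects remain.

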2.3 Procedures

A baseline assessment of the following domains will be conducted: cognitive function, gross motor and fine motor function, and mood/psycho-social function. Because the PHQ9 assessment asks a question regarding suicide ideality, we will promptly review it each time it is completed, and if suicide ideality is reported, the subject will be provided with appropriate resources.

Participants will start a daily regimen of Amantadine: dosing of 2-5 mg/kg divided by two daily doses (max daily dose of 300 mg). Participants and caregivers will be given a diary to document their perceived effects of Amantadine. At 3 and 6 weeks, we will repeat the assessments done in the pre-test to evaluate efficacy of Amantadine.

2.4 Statistical Analysis

No power calculations were made since there is no previous study that used the same population (adolescents and adults), with the same intervention (Amantadine), to find the same outcomes (cognitive and motor function).

The results will be statistically analyzed by using the paired samples t-test on SPSS.

2.5 Potential Risks

Possible adverse reactions to Amantadine: The adverse reactions reported most frequently at the recommended dose of SYMMETREL (5--10%) are: nausea, dizziness (lightheadedness), and insomnia. Less frequently (1-5%) reported adverse reactions are: depression, anxiety and irritability, hallucinations, confusion, anorexia, dry mouth, constipation, ataxia, livedo reticularis, peripheral edema, orthostatic hypotension, headache, somnolence, nervousness, dream abnormality, agitation, dry nose, diarrhea and fatigue.

Infrequently (0.1-1%) occurring adverse reactions are: congestive heart failure, psychosis, urinary retention, dyspnea, skin rash, vomiting, weakness, slurred speech, euphoria, thinking abnormality, amnesia, hyperkinesia, hypertension, decreased libido, and visual disturbance, including punctate subepithelial or other corneal opacity, corneal edema, decreased visual acuity, sensitivity to light, and optic nerve palsy. Rare (less than 0.1%) occurring adverse reactions are: instances of convulsion, leukopenia, neutropenia, eczematoid dermatitis, oculogyric episodes, suicidal attempt, suicide, and suicidal ideation.

Possible risks from assessments: There are minor risks associated with performing the physical assessments listed in this study. During the cognitive and manual assessments, the patient may become fatigued. The study team will advise the test and instruct the patient to rest if signs of fatigue. The patient may rest or terminate the test at any point if they become too fatigued.

2.6 Data Handling and Monitoring

All study data will be collected and stored in a secure and locked filing cabinet that only the research coordinator has the key to, in the locked and secure office of the research coordinator in Harkness Pavilion. The data will also be securely stored on REDCap and CUIMC OneDrive, an encrypted and secure online database that only the Principal Investigator and co-investigators will be given access to.

Patient data and safety will be monitored locally by implementing monthly meetings involving all personnel who are working on the study in order to ensure appropriate data management and patient confidentiality. Data and patient PHI will be stored in a locked cabinet in a locked office only accessible to the study team, and on a secure and encrypted online database that only the study team will have access to.
